11.0 MEASUREMENT OF EFFECT

Response and progression will be evaluated in this study using the new international criteria proposed by the revised Response Evaluation Criteria in Solid Tumors (RECIST) guidelines (version 1.1) [38]. Changes in the largest diameter (unidimensional measurement) of the tumor lesions and the short axis measurements in the case of lymph nodes are used in the RECIST guideline.

11.1 Schedule of Evaluations

Restaging cross sectional imaging studies are performed as scheduled throughout the study timeline:

- Prior to treatment (includes real-time central review),
- Following 4 cycles of neoadjuvant chemotherapy,
- Following either 4 cycles of neoadjuvant chemotherapy but before surgery (Arm 1) or following 3 cycles of neoadjuvant chemotherapy and radiation but before surgery (Arm 2) (Note: Arm 2 closed to new patient enrollment on 08/13/2018)
- Following surgery but prior to postoperative chemotherapy
- Following 4 cycles of adjuvant chemotherapy

Surveillance is per the schedule outlined in the Study Calendar in [Section 5.0](#).

Supporting documentation of surgical and pathologic response and progression should be submitted per [Section 6.1.1](#).

11.2 Definitions of Measurable and Non-measurable Disease

11.2.1 Measurable Disease

A non-nodal lesion is considered measurable if its longest diameter can be accurately measured as ≥ 2.0 cm with chest X-ray, or as ≥ 1.0 cm with CT scan or MRI.

A superficial non-nodal lesion is measurable if its longest diameter is ≥ 1.0 cm in diameter as assessed using calipers (e.g. skin nodules) or imaging. In the case of skin lesions, documentation by color photography, including a ruler to estimate the size of the lesion, is recommended.

A malignant lymph node is considered measurable if its short axis is ≥ 1.5 cm when assessed by CT scan (CT scan slice thickness recommended to be no greater than 5 mm).

11.2.2 Non-measurable Disease

All other lesions (or sites of disease) are considered non-measurable disease, including pathological nodes (those with a short axis ≥ 1.0 to < 1.5 cm). Bone lesions, leptomeningeal disease, ascites, pleural/pericardial effusions, lymphangitis cutis/pulmonis, inflammatory breast disease, and abdominal masses (not followed by CT or MRI), are considered as non-measurable as well.

Note: 'Cystic lesions' thought to represent cystic metastases can be considered as measurable lesions, if they meet the definition of measurability described above. However, if non-cystic lesions are present in the same patient, these are preferred for selection as target lesions. In addition, lymph nodes that have a short axis < 1.0 cm are considered non-pathological (i.e. normal) and should not be recorded or followed.

11.3 Guidelines for Evaluation of Measurable Disease

11.3.1 Measurement Methods:

- All measurements should be recorded in metric notation (i.e. decimal fractions of centimeters) using a ruler or calipers.
- The same method of assessment and the same technique must be used to characterize each identified and reported lesion at baseline and during follow-up. For patients having only lesions measuring at least 1 cm to less than 2 cm must use CT imaging for both pre- and post-treatment tumor assessments.
- Imaging-based evaluation is preferred to evaluation by clinical examination when both methods have been used at the same evaluation to assess the antitumor effect of a treatment.

11.3.2 Acceptable Modalities for Measurable Disease:

- **Conventional CT and MRI:** This guideline has defined measurability of lesions on CT scan based on the assumption that CT slice thickness is 3 mm or less.

As with CT, if an MRI is performed, the technical specifications of the scanning sequences used should be optimized for the evaluation of the type and site of disease. The lesions should be measured on the same pulse sequence. Ideally, the same type of scanner should be used and the image

acquisition protocol should be followed as closely as possible to prior scans. Body scans should be performed with breath-hold scanning techniques, if possible.

- **Chest X-ray:** Lesions on chest X-ray are acceptable as measurable lesions when they are clearly defined and surrounded by aerated lung. However, CT scans are preferable.

11.3.3 Measurement at Follow-up Evaluation:

- The cytological confirmation of the neoplastic origin of any effusion that appears or worsens during treatment when the measurable tumor has met criteria for response or stable disease is mandatory to differentiate between response or stable disease (an effusion may be a side effect of the treatment) and progressive disease.
- Cytologic and histologic techniques can be used to differentiate between PR and CR in rare cases (e.g. residual lesions in tumor types such as germ cell tumors, where known residual benign tumors can remain.)

11.4 Measurement of Treatment/Intervention Effect

11.4.1 Target Lesions & Target Lymph Nodes

- Measurable lesions (as defined in [Section 11.2.1](#)) up to a maximum of 5 lesions, representative of all involved organs, should be identified as “Target Lesions” and recorded and measured at baseline. These lesions can be non-nodal or nodal (as defined in [Section 11.2.1](#)), where no more than 2 lesions are from the same organ and no more than 2 malignant nodal lesions are selected.

Note: If fewer than 5 target lesions and target lymph nodes are identified (as there often will be), there is no reason to perform additional studies beyond those specified in the protocol to discover new lesions.

- Target lesions and target lymph nodes should be selected on the basis of their size, be representative of all involved sites of disease, but in addition should be those that lend themselves to reproducible repeated measurements. It may be the case that, on occasion, the largest lesion (or malignant lymph node) does not lend itself to reproducible measurements in which circumstance the next largest lesion (or malignant lymph node) which can be measured reproducibly should be selected.
- **Baseline Sum of Dimensions (BSD):** A sum of the longest diameter for all target lesions plus the sum of the short axis of all the target lymph nodes will be calculated and reported as the baseline sum of dimensions (BSD). The BSD will be used as reference to further characterize any objective tumor response in the measurable dimension of the disease.
- **Post-baseline Sum of the Dimensions (PBSD):** A sum of the longest diameter for all target lesions plus the sum of the short axis of all the target lymph nodes will be calculated and reported as the post-baseline sum of dimensions (PBSD). If the radiologist is able to provide an actual measure for the target lesion (or target lymph node), that should be recorded, even if it is below 0.5 cm. If the target lesion (or target lymph node) is believed to be present and is faintly seen but too small to measure, a default value of 0.5 cm should be assigned. If it is the opinion of the radiologist that the

target lesion or target lymph node has likely disappeared, the measurement should be recorded as 0 cm.

- **The minimum sum of the dimensions (MSD)** is the minimum of the BSD and the PBSD.

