11.4.3 Response Criteria

All target lesions and target lymph nodes followed by CT/MRI/Chest X-ray/physical examination must be measured on re-evaluation at the evaluation time points specified in [Section 11.1](#). Specifically, a change in objective status to either a PR or CR cannot be done without re-measuring target lesions and target lymph nodes.

Note: Non-target lesions and non-target lymph nodes should be evaluated at each assessment, especially in the case of first response or confirmation of response. In selected circumstances, certain non-target organs may be evaluated less frequently. For example, bone scans may need to be repeated only when complete response is identified in target disease or when progression in bone is suspected.

Evaluation of Target Lesions

Complete Response (CR): All of the following must be true:

- Disappearance of all target lesions.
- Each target lymph node must have reduction in short axis to < 1.0 cm.

Partial Response (PR): At least a 30% decrease in PBSD (sum of the longest diameter for all target lesions plus the sum of the short axis of all the target lymph nodes at current evaluation) taking as reference the BSD (see [Section 11.4.1](#)).

Progression (PD): At least one of the following must be true:

- At least one new malignant lesion, which also includes any lymph node that was normal at baseline (< 1.0 cm short axis) and increased to ≥ 1.0 cm short axis during follow-up.
- At least a 20% increase in PBSD (sum of the longest diameter for all target lesions plus the sum of the short axis of all the target lymph nodes at current evaluation) taking as reference the MSD ([Section 11.4.1](#)). In addition, the PBSD must also demonstrate an absolute increase of at least 0.5 cm from the MSD.

Stable Disease (SD): Neither sufficient shrinkage to qualify for PR, nor sufficient increase to qualify for PD taking as reference the MSD.

Evaluation of Non-target Lesions & Non-target Lymph Nodes

Complete Response (CR): All of the following must be true:

- Disappearance of all non-target lesions.
- Each non-target lymph node must have a reduction in short axis to <1.0 cm.

Non-CR/Non-PD: Persistence of one or more non-target lesions or non-target lymph nodes.

Progression (PD): At least one of the following must be true:

- a. At least one new malignant lesion, which also includes any lymph node that was normal at baseline (< 1.0 cm short axis) and increased to ≥ 1.0 cm short axis during follow-up.

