11.4.3.1 Evaluation of Elevated CA19-9 Levels (When Present)

Note: this evaluation will be done for each patient for descriptive purposes only and will not be used to evaluate the secondary endpoint of progression free survival. Decision making for the efficacy of therapy and for relapse or progression must be based on imaging. Biochemical progression without the demonstration of objective progression of target or non-target lesion will not be sufficient indication to remove the patient from the study (refer to [Section 13.1](#)).

Biochemical Response (B-RESP): Reduction in elevated CA 19-9 level by at least 50% of normalization of an elevated value, confirmed with 2 successive measures.

Biochemical Progression (B-PROG): Increase in elevated CA 19-9 level by 50%, confirmed with 2 successive measures. If patient has had biochemical response as defined above, then subsequent biochemical progression is defined as >50% increase from the lowest recorded level while on study.

Biochemical Stability (B-STAB): Elevated CA 19-9 level does not change enough to qualify as response or progression.

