13.1.2.2 Event-free Survival

Event-free survival is defined as time from randomization to the first documentation of event where events considered are 1) disease progression, per RECIST, prior to surgery, 2) surgery with R2 resection, 3) recurrent disease following surgery, or 4) death due to any cause.

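### As written, the MSD formula reduces to a baseline-only reference for target-lesion progression, so regrowth from an earlier low point can escape event 1 of event-free survival

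*Combined protocol and SAP*

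**What the plan says.** Section 11.4.1 defines a baseline sum of dimensions (BSD) and a post-baseline sum (PBSD), then states that the MSD "is the minimum of the BSD and the PBSD". PBSD is singular, and neither a nadir nor earlier evaluations are mentioned.

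Section 11.4.3 sets two conditions for progressive disease (PD) by target-lesion size. The first is "At least a 20% increase in PBSD", where PBSD is the sum "at current evaluation) taking as reference the MSD". The second is that "the PBSD must also demonstrate an absolute increase of at least 0.5 cm from the MSD". Stable disease also refers to the MSD, while partial response refers to the BSD.

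Other routes to PD do not use the MSD. One is "At least one new malignant lesion, which also includes any lymph node that was normal at baseline"; another is unequivocal non-target progression.

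Section 13.1.2.2 makes "disease progression, per RECIST, prior to surgery" the first EFS event. Section 11.0 adopts RECIST version 1.1. For CA 19-9, section 11.4.3.1 defines biochemical progression after a response as a rise of more than 50%, measured as an "increase from the lowest recorded level while on study".

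**The concern.** A progression reference that carries the name minimum sum should remember the smallest tumour burden seen so far. The formula in 11.4.1, combined with the meaning given to PBSD in 11.4.3, compares the current sum with itself whenever the tumour is at or below its baseline size. A tumour that shrinks and then regrows could therefore be recorded as stable, or even as a continuing response, when it would be PD measured from its low point.

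What is at stake is the first component of EFS, a named secondary objective. Any error from the literal rule runs one way: PD by size is declared later or not at all, and EFS looks longer. Two programmers or sites could also classify the same measurements differently, depending on how they read one sentence.

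**Working it through.** The documents give no event count, power or progression rate for EFS, so there is no plan figure to reproduce. The check is of the rule itself.

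**Inputs.** MSD formula: 11.4.1. PBSD as the current sum, and the 20% and 0.5 cm thresholds: 11.4.3. Scan times: section 5.0. Lesion sizes below are assumed, because the documents give none.

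**Step 1: what the formula does.** Let B be the baseline sum and C the current sum, so that literally MSD = min(B, C).
- If C ≤ B, then MSD = C and C − MSD = 0. PD by size is impossible.
- If C > B, then MSD = B. PD requires C ≥ 1.2 × B and C − B ≥ 0.5 cm.

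Both cases match a rule whose reference is simply B. A grid of B from 1.0 to 10.0 cm and C from 0.1 to 15.0 cm gave no disagreement between the two.

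**Step 2: thresholds.** For a reference R, PD by size needs C ≥ max(1.2 × R, R + 0.5).
- Literal, B = 4.0: max(4.8, 4.5) = 4.8 cm. Exceeding baseline is not enough; 4.1 and 4.5 cm are still not PD.
- Low point 2.8: max(3.36, 3.3) = 3.36 cm.
- Low point 2.0: max(2.4, 2.5) = 2.5 cm.

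From a low point of 2.8 cm, the literal rule needs growth of 4.8 / 2.8 − 1 = 71%; a low-point reference needs 20%.

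**Step 3: records (cm).**

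| Baseline, scan 1, scan 2 | From low point | As written |
|---|---|---|
| 4.0, 2.8, 3.5 | +25%, +0.7: PD | reference 3.5, +0%: not PD |
| 3.0, 2.0, 3.4 | +70%, +1.4: PD | reference 3.0, +13%, +0.4: not PD |
| 4.0, 3.0, 3.7 | +23%, +0.7: PD | reference 3.7, +0%: not PD |
| 3.0, 3.0, 3.7 | +23%, +0.7: PD | reference 3.0, +23%, +0.7: PD |

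The third record shrank by 25%, short of the 30% for partial response, so the issue is not confined to responders.

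**Step 4: where the readings can differ.** At the first restaging scan the only earlier sum is baseline, so they agree. Section 5.0 schedules one more scan before surgery, and that one can differ. Later scans matter only in patients who never have surgery, expected to be 40% in section 13.2 (0.40 × 134 = 53.6, about 54 at full accrual). Whether those scans happen is unclear: the section 5.0 footnote gives scans every 16 weeks after treatment, but for patients removed from protocol treatment it asks for survival information every 6 months.

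**Step 5: can the effect on EFS be sized?** Only by assuming growth rates. Take baseline sums of 3.0, 3.5 and 4.5 cm and a log change to the first scan of mean −0.15, SD 0.20. Vary the log change to the second scan, and use the planned 62 evaluable patients per arm as a scale:
- mean 0, SD 0.20: 5.7 to 6.5 of 62 size-based PDs missed (40 to 43% of them);
- mean 0, SD 0.10: 1.1 to 1.5 of 62 (18 to 23%);
- mean −0.05, SD 0.10: fewer than 0.5 of 62 (8 to 10%).

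The first set gives a best response rate of 28% and the third 26%. Both are close to the pilot's 6 of 22 (27%, section 1.4.4), so matching the pilot does not settle the answer.

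**The case against.** The strongest reply is that the literal reading is not the only one. The PBSD definition in 11.4.1 does not contain the word current; that comes from the parenthesis in 11.4.3. The MSD sentence can be read as the minimum over baseline and all post-baseline sums, and then 4.0, 2.8, 3.5 cm is PD and nothing is lost. The term minimum sum supports this. So does using MSD for PD but BSD for partial response, a distinction without effect under the literal formula. RECIST 1.1 is adopted by reference, and EFS event 1 is stated per RECIST.

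That stands as evidence of intent, and it rules out asserting that EFS is overstated. It does not rescue the wording: 11.4.3 says which PBSD it means, no other section states a nadir for tumour sums, and the CA 19-9 rule shows that the authors wrote a low point explicitly when they specified one.

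A second reply is that much progression is not by size. In section 1.4.8, metastatic disease was the commonest reason for no resection, and 1 of 176 patients had isolated local progression that precluded surgery. Those patients had resectable disease, so the evidence is indirect. In the pilot, 6 of 22 patients (27%) went unresected because of progression of any kind. The first assumption set in the working gives 22 to 24% by target size alone, which leaves little room for new lesions. A reader might infer from that set that about 40% of size-based progressions would be lost; the documents do not support a figure.

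**Conclusion.** The MSD sentence is wrong as written. Taken with 11.4.3, it makes the target-lesion PD reference equivalent to baseline, so PD by size needs at least 20% and at least 0.5 cm above baseline, and regrowth from any earlier low point that stays below that level is not PD. This conflicts with the plan's evident intent.

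The consequence is conditional. If the sentence is applied literally, size-based PD before surgery would be delayed or missed at the pre-surgical scan, and at any later scan in a patient without surgery, and EFS would be lengthened. The direction is certain under that condition; the size cannot be estimated from the documents.

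Several stronger conclusions might be inferred and are not supported. Nothing shows that sites or programmers use the literal formula. The effect is not limited to responders. It does not reach PD by new or non-target lesions, R2 resection, recurrence after surgery or death, all of which count without the MSD. The 18-month overall survival endpoint and the R0 interim rule do not use it. Counts per 62 patients are only a scale, since Arm 2 closed to enrolment and its treatment ceased on 08/13/2018. This is a correction to a secondary endpoint's event definition, worth making because it is directional and cheap.

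**What to change.** In section 11.4.1, replace the MSD sentence with: *MSD is the smallest sum of dimensions recorded at baseline or at any evaluation before the current one.* Use this MSD for the target-lesion size criterion of PD in 11.4.3 when deriving EFS event 1. Leave the new-lesion and non-target criteria as they are, so that overall status still combines all three.

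The cost is one sentence and a small change to the EFS derivation program. The sums are already to be recorded at each evaluation, so EFS can be derived retrospectively without new data. EFS may become slightly less favourable than under the literal rule; if the low point was already being used, nothing changes.

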11.4.2 Non-target Lesions & Non-target Lymph Nodes

Non-measurable sites of disease ([Section 11.2.2](#)) are classified as non-target lesions or non-target lymph nodes and should also be recorded at baseline. These lesions and lymph nodes should be evaluated in accordance with [Section 11.4.3](#).

11.4.3 Response Criteria

All target lesions and target lymph nodes followed by CT/MRI/Chest X-ray/physical examination must be measured on re-evaluation at the evaluation time points specified in [Section 11.1](#). Specifically, a change in objective status to either a PR or CR cannot be done without re-measuring target lesions and target lymph nodes.

Note: Non-target lesions and non-target lymph nodes should be evaluated at each assessment, especially in the case of first response or confirmation of response. In selected circumstances, certain non-target organs may be evaluated less frequently. For example, bone scans may need to be repeated only when complete response is identified in target disease or when progression in bone is suspected.

Evaluation of Target Lesions

Complete Response (CR): All of the following must be true:

- Disappearance of all target lesions.
- Each target lymph node must have reduction in short axis to < 1.0 cm.

Partial Response (PR): At least a 30% decrease in PBSD (sum of the longest diameter for all target lesions plus the sum of the short axis of all the target lymph nodes at current evaluation) taking as reference the BSD (see [Section 11.4.1](#)).

Progression (PD): At least one of the following must be true:

- At least one new malignant lesion, which also includes any lymph node that was normal at baseline (< 1.0 cm short axis) and increased to ≥ 1.0 cm short axis during follow-up.
- At least a 20% increase in PBSD (sum of the longest diameter for all target lesions plus the sum of the short axis of all the target lymph nodes at current evaluation) taking as reference the MSD ([Section 11.4.1](#)). In addition, the PBSD must also demonstrate an absolute increase of at least 0.5 cm from the MSD.

Stable Disease (SD): Neither sufficient shrinkage to qualify for PR, nor sufficient increase to qualify for PD taking as reference the MSD.

Evaluation of Non-target Lesions & Non-target Lymph Nodes

Complete Response (CR): All of the following must be true:

- Disappearance of all non-target lesions.
- Each non-target lymph node must have a reduction in short axis to <1.0 cm.

Non-CR/Non-PD: Persistence of one or more non-target lesions or non-target lymph nodes.

Progression (PD): At least one of the following must be true:

- a. At least one new malignant lesion, which also includes any lymph node that was normal at baseline (< 1.0 cm short axis) and increased to ≥ 1.0 cm short axis during follow-up.
- b. Unequivocal progression of existing non-target lesions and non-target lymph nodes. (NOTE: Unequivocal progression should not normally trump target lesion and target lymph node status. It must be representative of overall disease status change.)

11.4.3.1 Evaluation of Elevated CA19-9 Levels (When Present)

Note: this evaluation will be done for each patient for descriptive purposes only and will not be used to evaluate the secondary endpoint of progression free survival. Decision making for the efficacy of therapy and for relapse or progression must be based on imaging. Biochemical progression without the demonstration of objective progression of target or non-target lesion will not be sufficient indication to remove the patient from the study (refer to [Section 13.1](#)).

Biochemical Response (B-RESP): Reduction in elevated CA 19-9 level by at least 50% of normalization of an elevated value, confirmed with 2 successive measures.

Biochemical Progression (B-PROG): Increase in elevated CA 19-9 level by 50%, confirmed with 2 successive measures. If patient has had biochemical response as defined above, then subsequent biochemical progression is defined as >50% increase from the lowest recorded level while on study.

Biochemical Stability (B-STAB): Elevated CA 19-9 level does not change enough to qualify as response or progression.

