2.2 Secondary Objectives

- 2.2.1 To evaluate and estimate the R0 resection rates in patients receiving each of the two multimodality treatment regimens.
- 2.2.2 To evaluate and estimate the event-free survival in patients receiving each of the two multimodality treatment regimens.
- 2.2.3 To evaluate and estimate the pathologic complete response (pCR) rates in patients receiving each of the two multimodality treatment regimens
- 2.2.4 To assess the adverse events (AE) profile and safety of each treatment arm, using the CTCAE and PRO-CTCAE.

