13.4.2 Secondary Endpoints

13.4.2.1 Event-free Survival

The distribution of event-free survival will be estimated using the method of Kaplan-Meier in each arm. Event-free survival will be compared between treatment groups using the log-rank test. The correlation between pCR status and event-free survival time will be assessed by Cox model with landmark approach.

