13.4.2.2 R0 Resection Rate

R0 resection rate and confidence intervals for the R0 resection rate will be calculated according to the approach of Duffy and Santner. Chi-square test (or Fisher's exact test if the data in contingency table is sparse) will be used to compare R0 resection rate between treatment arms. Sensitivity analysis will be conducted among patients in cohort 1) and cohort 2). The association between R0 resection rate and OS/PFS will be assessed by log-rank test and Cox model.

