13.4.2.3 Pathologic Complete Response (pCR) Rate

pCR rate and confidence intervals for the pCR rate will be calculated according to the approach of Duffy and Santner. Chi-square test (or Fisher's exact test if the data in contingency table is sparse) will be used to compare pCR resection rate between two treatment arms. Sensitivity analysis will be conducted among patients in cohort 1) and cohort 2). The association between pCR rate and OS/PFS will be assessed by log-rank test and Cox model.

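### R0 and pCR are tested against a PFS that Section 13 never defines; if PFS is read as EFS, an R2 resection is both the unfavourable exposure and the event

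*Combined protocol and SAP*

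**What the plan says.** The secondary objective in 2.2.2 is event-free survival: "To evaluate and estimate the event-free survival in patients receiving each of the two multimodality treatment regimens". Section 13.1.2.2 defines it: "Event-free survival is defined as time from randomization to the first documentation of event", where the "events considered are 1) disease progression, per RECIST, prior to surgery, 2) surgery with R2 resection, 3) recurrent disease following surgery", or death from any cause. Section 13.4.2.1 analyses EFS and adds: "The correlation between pCR status and event-free survival time will be assessed by Cox model with landmark approach". It gives no landmark time.

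Elsewhere the name changes. Section 11.4.3.1 says that CA19-9 changes "will not be used to evaluate the secondary endpoint of progression free survival". Section 13.4.2.2 states: "The association between R0 resection rate and OS/PFS will be assessed by log-rank test and Cox model". Section 13.4.2.3 states: "The association between pCR rate and OS/PFS will be assessed by log-rank test and Cox model". Section 14.2.3 also relates the NAUC ratio to progression-free survival. Section 11.5 sends the reader to the statistical section for formal definitions, but that section gives PFS no event list, start date or censoring rule.

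Section 11.7.2 makes R2 a class of its own, separate from R0. Section 13.1.2.1 sets two cohorts for the R0 rate, all treated patients (cohort 1) and operated patients (cohort 2). Section 13.1.2.3 does the same for pCR.

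**The concern.** An analyst who reaches 13.4.2.2 must decide what PFS is. The only composite with a definition is EFS, and EFS treats R2 resection as an event. A test of R0 against that endpoint contains patients who are in the comparison group because of their R2 status and have an event for the same reason. Part of any R0 benefit would then be true by definition. The same applies to pCR, because a patient with known or suspected gross tumor left behind would not be counted as a pCR.

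At stake is the interpretation of two planned secondary association analyses. A hazard ratio favouring R0 or pCR could be reported as a finding about the disease when some of it comes from the endpoint definition.

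**Working it through.** The plan states no power, event count or effect size for EFS or PFS, so there is no figure to reproduce. The check sets the sections side by side and then sizes the overlap under stated assumptions.

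**1. Two readings of PFS**

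- PFS is a separate endpoint. It is then undefined in three planned analyses (13.4.2.2, 13.4.2.3, 14.2.3).
- PFS means EFS. Then 13.4.2.1 (Cox with landmark) and 13.4.2.3 (log-rank and Cox, no landmark stated) give two methods for one pCR question, and the overlap below arises.

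**2. Exposure against event, reading PFS as EFS**

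| Patient | R0 group | EFS event by definition? |
|---|---|---|
| R0 resection | R0 | No |
| R1 resection | not R0 | No |
| R2 resection | not R0 | Yes, no later than surgery |
| Progressed before surgery, never resected (cohort 1 only) | not R0 | Yes, at progression |

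The R1 row shows the limit: only part of the not-R0 group has an automatic event. The last row does not depend on the R2 item, because progression before surgery would count under an ordinary PFS too. Section 13.2 expects 40% not to reach surgery, though not all because of progression.

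**3. Effect on the log-rank test**

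Take 74 operated patients, 12 of them not R0, including 2 R2, with the clock starting at surgery. At time zero there are d = 2 events, both in the not-R0 group.

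- Expected in that group: 2 × 12/74 = 0.32. Observed: 2. Difference: 1.68.
- Variance: 2 × (12/74) × (62/74) × (72/73) = 0.27.

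With 60 R0, 10 R1 and 4 R2, the expected number is 4 × 14/74 = 0.76, the difference 3.24 and the variance 4 × (14/74) × (60/74) × (70/73) = 0.59. This excess is present before any follow-up.

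**4. Size under assumed counts**

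Inputs from the plan: 60% of evaluable patients reach surgery (13.2), so 0.6 × 124 = 74 under the two-arm plan and 0.6 × 62 = 37 in one arm. Assumed: the R0, R1 and R2 counts; exponential time to recurrence or death with a 14-month median from surgery in every patient, so no true link with margin status; uniform censoring at 13–45 months; R2 events at time zero. An R0 benefit is counted when the log-rank z exceeds 1.96, and HR = exp(U/V).

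| R0 / R1 / R2 | Total | Median HR, not R0 vs R0 | Nominal R0 benefit |
|---|---|---|---|
| 62 / 12 / 0 | 74 | 1.0 | about 4% |
| 62 / 11 / 1 | 74 | 1.14 | 7% |
| 62 / 10 / 2 | 74 | 1.30 | 12–13% |
| 60 / 10 / 4 | 74 | 1.65 | 27% |
| 62 / 10 / 4 | 76 | 1.64 | 26–28% |
| 31 / 5 / 1 | 37 | 1.32–1.35 | 11–12% |

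Dropping the R2 patients returns the rate to about 4% and the HR to 1.01.

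A second set of assumptions (12-month median, follow-up 12–36 months, 15% not R0 in total, two-sided 5% test) points the same way. With 74 operated, the false-positive rate is 5–6% when R2 is not an event. It is about 12%, 35% and 84% when 2%, 5% and 10% of operated patients are R2. With 37 operated, it is about 7%, then 12%, 29% and 66%.

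**5. What is not touched**

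The final rule in 13.4.1.2 counts patients alive at 18 months, and the interim rule in 13.4.1.1 counts R0 resections. Neither uses EFS or PFS.

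**The case against.** The strongest reply is that the R2 overlap is conditional. The documents never say that PFS means EFS. If PFS is plain progression or death, R2 is not an event, and since progression (11.4.3) and recurrence (11.8) are defined, all that is missing is one definition. This stands for the R2 overlap. It does not answer the missing time origin or the cohort 1 overlap.

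A second reply is that a landmark removes patients with an event on or before it, as the pCR analysis in 13.4.2.1 may already do. That is right, and excluding R2 patients does restore the error rate. But 13.4.2.2 and 13.4.2.3 state no landmark, and starting the clock at surgery is not enough if time-zero events are kept.

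Third, R2 may be rare. In the pilot described in 1.4.4, 14 of 15 operations had negative margins, so zero or one R2 patient is plausible. Also, 74 operated patients belongs to the original two-arm plan, and Arm 2 closed on 08/13/2018. Both points stand and limit the size.

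A reader might infer that the R0 association is meant to validate R0 as the futility measure, so that a circular result would vindicate the interim rule. No section says so. The association is not a listed objective, and the same sentence in 13.4.2.2 also tests OS, where R2 is not an event.

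A reader might also take the pointer to Section 13.1 in 11.4.3.1 as a failed reference to a PFS definition. It follows the sentence on removing patients from the study, and the CA19-9 instruction is the same under either name.

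**Conclusion.** The point holds in limited form. Without any condition, PFS is used in planned analyses and never defined, and the R0 and pCR associations have no stated time origin or landmark. On condition that PFS is read as EFS, every R2 patient is both unexposed and an event at surgery, which favours R0 and pCR. If cohort 1 is used, patients who progress and are never resected add to this.

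The direction is clear; the size is not, because the plan gives no R2 rate. The rates of about 4%, 7%, 12–13% and 26–28% for none, one, two and four R2 patients illustrate assumed counts and do not predict this trial's results. The primary endpoint, the 62 per arm and the interim rule are unaffected.

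A tempting conclusion is that replacing PFS by EFS throughout would settle the matter. It would not: in 13.4.2.3 it would build in the R2 overlap for pCR and leave two methods for the analysis that 13.4.2.1 already specifies.

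**What to change.** 1. In 13.4.2.2, assess R0 in operated patients from the date of surgery, using OS and recurrence-or-death, comparing R0 with R1. Describe R2 patients separately.
2. In 13.4.2.3, use the same time origin and exclude R2 patients, or do not count R2 as an event. Align the text with the landmark Cox model in 13.4.2.1, so that one method applies to pCR.
3. In 11.4.3.1, use the EFS name. In 14.2.3, either use EFS or define PFS in 13.1.

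The cost is wording only: no new data and no change to the primary analysis. The downside is that the few R2 patients leave the association models. Operated patients without an R0 or R1 class, such as those with an aborted operation, also fall outside the R0-versus-R1 comparison and should be counted in the description.
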